2.1. Study Rationale

The purpose of this study is to evaluate the safety, tolerability and PK of single ascending oral doses of PF-06954522 in healthy adult participants. This study is the first time that PF-06954522 will be administered to humans. The safety, tolerability and PK results obtained from this study will inform future clinical development of PF-06954522.

2.2. Background

[figure not shown]
Diabetes is estimated to affect more than 500 million adults (aged 20-79) worldwide.[5] The increase in the global prevalence of T2DM is largely attributed to rising rates of excess body weight and obesity.[6] T2DM is characterized by insulin resistance, a disorder in which cells do not respond effectively to insulin, resulting in higher blood glucose levels. Elevated blood glucose levels and increasing severity of insulin resistance result in the need for more insulin over time, eventually resulting in progressive pancreatic β -cell failure.[7] Patients with poorly controlled T2DM have an increased risk of developing complications associated with both microvascular and macrovascular disease, including nephropathy, neuropathy, retinopathy, and cardiovascular disease; and are at 2 to 4 times increased risk of mortality when compared with adults who do not have diabetes.[8] While existing pharmacological options for the treatment of diabetes may provide satisfactory glycemic control for some patients, there remain a large number of patients who do not achieve target HbA1c levels, suggesting a need for additional therapeutic options which minimize patient burden such as oral therapies.

Currently available GLP-1R agonists have demonstrated robust efficacy for glycemic control, weight loss, and CV safety, with several agents having shown a benefit in CV outcomes.[9] Most available GLP-1R agonist treatment options are injected once weekly subcutaneously.[10],[11] Injectable therapies are often underutilized due to patient hesitancy, whereas oral options are preferred by many patients. Only one GLP-1R agonist (Rybelsus®; oral semaglutide) is currently commercially available for oral administration. However, oral semaglutide has strict administration requirements (food and water restrictions) and has limitations due to its low bioavailability[12], making it less convenient than an agent without such restrictions. A novel oral small molecule GLP-1R agonist that may further improve glycemic control, reduce HbA1c levels, and decrease food intake and body weight compared to existing oral GLP-1R agonist, without any administration restrictions, is expected to be a preferred therapeutic option for patients with T2DM and their physicians. Another small

molecule GLP-1R agonist (danuglipron) is also currently under development by Pfizer for the treatment of T2DM.

[figure not shown]
Brief summaries of nonclinical pharmacology, nonclinical PK and metabolism, biopharmaceutical properties and nonclinical safety are provided below. Additional details for these sections can be found in the IB.

2.2.1. Nonclinical Pharmacology

[figure not shown]
2.2.2. Nonclinical Pharmacokinetics and Metabolism

In rats and monkeys following single IV and oral dosing, PF-06954522 exhibited low CL_p and low to moderate steady state V_{ss}, leading to a Renal and biliary excretion of unchanged PF-06954522 was minimal in rats. After repeated oral doses of PF-06954522 to rats and monkeys, systemic exposure increased with increasing dose, with little to no accumulation observed.

[figure not shown]

Preliminary in vitro metabolism of PF-06954522 showed similar metabolic profiles in monkey and human with some differences in mouse, rat, rabbit, and dog and no evidence of human specific metabolites.

Based on the regulatory FDA

2.2.3. Biopharmaceutics

[figure not shown]

[figure not shown]
2.2.4. Nonclinical Safety

PF-06954522 has been evaluated in nonclinical safety studies up to 8 weeks in rats and monkeys.

associated with nonadverse changes in hematology (increased reticulocytes) and nonadverse microscopic findings in the thymus (decreased lymphocyte cellularity), peri-aortic adipose tissue (decreased lipid content), and pancreas (decreased zymogen content). Nonadverse findings noted in animals surviving to scheduled necropsy included decreased food consumption, body weight and body condition score, decreased total triiodothyronine (without changes in thyroxine or thyroid stimulating hormone), and sporadic emesis.

PF-06954522 was not genotoxic in either in vitro or in vivo assays. There is no photo safety concern with PF-06954522.

2.3. Benefit/Risk Assessment

Study C4001001 is the first time that PF-06954522 will be administered to humans. For healthy participants participating in this single dose study, no clinical benefit is expected. The purpose of this study is to evaluate the safety, tolerability, and PK of single ascending oral doses of PF-06954522 in healthy adult participants; and provide the basis for further clinical development of PF-06954522 as a potential new, pharmacological agent for the

treatment of patients with T2DM. As of the date of this protocol, no specific human risks have been identified; postulated risks based on nonclinical studies with PF-06954522 and marketed GLP-1R agonists are summarized in Section 2.3.1. The clinical impact of any potential risks will be minimized through the proposed cautious dose escalation process wherein higher doses of PF-06954522 will be administered only after lower doses have been found to be well tolerated with an acceptable safety profile (Section 4.2 and Section 4.3). In addition, this study will employ stopping rules for dose escalation (Section 6.6.1) and includes standard, intensive, inpatient monitoring of the participants following administration of single, oral doses of the study intervention as outlined in the SoA.

More detailed information about the known and expected benefits and risks and reasonably expected AEs of PF-06954522 may be found in the IB, which is the SRSD for this study. Refer to the Study Intervention(s) table in Section 6.1 for a complete description of SRSDs.

2.3.1. Risk Assessment

Potential Risk of Clinical Significance	Summary of Data/Rationale for Risk	Mitigation Strategy						
Study Intervention(s) PF-06954522								
Gastrointestinal adverse reactions	The potential risks are based on product labeling for injectable GLP-1R agonists (ie, liraglutide, exenatide, semaglutide and dulaglutide).	Study includes inpatient monitoring of the participants following administration of a single dose of the study intervention. Participants are monitored to prevent potential sequelae of any severe gastrointestinal reactions, eg, dehydration.						
Hypoglycemia	Clinical trials with injectable GLP-1R agonists have not demonstrated an increased risk for hypoglycemia. However, when administered in combination with anti-diabetic agents that are known to have an increased risk of hypoglycemia (such as insulin or sulfonylureas), an increased risk for hypoglycemia was observed.	The participants enrolled will not have diabetes and will not be receiving anti-diabetic agents. Study includes inpatient monitoring of the participants following administration of a single dose of the study intervention.						
Increased heart rate and decreased PR interval	Based on the product labeling for the injectable GLP-1R agonist liraglutide for obesity, mean increases in resting heart rate ranged 2 to 3 bpm in clinical trials, with some participants experiencing greater increases in resting heart rate, up to 10-20 bpm. Increased heart rate and decreased PR interval was observed in a single-dose NHP study of PF-06954522.	Study includes inpatient monitoring of the participants through periodic vital sign assessment, ECGs and telemetry following administration of a single dose of the study intervention.						
Other potential risks associated with long-term dosing of marketed GLP-1R agonists include thyroid C-cell tumors, pancreatitis, impairment in renal function, diabetic retinopathy complications, suicidal ideation/behavior and acute gallbladder disease.	These potential risks are based on product labeling for injectable GLP-1R agonists (ie, liraglutide, dulaglutide, exenatide and semaglutide).	This is a single dose study in healthy participants. Participants with a personal or family history of MTC or MEN2; with acute pancreatitis or a history of chronic pancreatitis are not eligible for study entry. Study includes inpatient monitoring and safety laboratory surveillance (eg, calcitonin, amylase, lipase, eGFR) of the						

Potential Risk of Clinical Significance	Summary of Data/Rationale for Risk	Mitigation Strategy						
Study Intervention(s) PF-06954522								
		participants following administration of a dose of the study intervention.						
Increased transaminases (eg, ALT & AST)	Elevated ALT and AST were observed in a subset of participants in the lotiglipron clinical studies following multiple dose administration.	Study includes inpatient monitoring and safety laboratory surveillance (eg, LFTs) of the participants following administration of a dose of the study intervention.						

2.3.2. Benefit Assessment

The participants in this study are not expected to obtain any specific benefit beyond contributing to the process of developing new therapies in an area of unmet need.

2.3.3. Overall Benefit/Risk Conclusion

Based on all available data on PF-06954522, as well as data available for other GLP-1-R agonists and considering the measures to minimize risk to study participants, the potential risks identified in association with PF-06954522 are justified by the anticipated benefits that may be afforded to participants with T2DM.

3. OBJECTIVES AND ENDPOINTS

Objectives	Endpoints
Primary:	Primary:
To evaluate the safety and tolerability of single oral doses of PF-06954522, administered to healthy adult participants.	Assessment of AEs, safety laboratory tests, vital signs (blood pressure, pulse rate, temperature), cardiac telemetry and standard 12-lead ECGs, and PE.
Secondary:	Secondary:
To characterize plasma PK of PF-06954522 following single oral doses of PF-06954522 administered to healthy adult participants.	PF-06954522 PK parameters: AUC _{last} , C _{max} , T _{max} , and if data permit, AUC _{inf} and t _½ .
Tertiary/Exploratory:	Tertiary/Exploratory:
To further characterize plasma PK of PF-06954522 following single oral doses of PF-06954522 administered to healthy adult participants.	Additional PF-06954522 PK parameters: AUC _{last} (dn), C _{max} (dn), and if data permit, AUC _{inf} (dn), CL/F, and V _z /F.
Optional: to characterize the effect of food (high-fat breakfast) on the plasma PK of PF-06954522 following single oral doses of PF-06954522 in healthy adult participants.	PF-06954522 PK parameters after a high-fat meal: AUC _{last} , C _{max} , T _{max} and if data permit, AUC _{inf} , CL/F, V _z /F and t _½ .
CCI	
Optional: to explore the safety, tolerability, and plasma PK of PF-06954522 in healthy adult Japanese participants.	Assessment of AEs, safety laboratory tests, vital signs (blood pressure, pulse rate and temperature), standard 12-lead ECGs and the following PF-06954522 PK parameters in Japanese participants: AUClast, Cmax, Tmax, and if data permit, AUCinf, CL/F, Vz/F and t½.

4. STUDY DESIGN

4.1. Overall Design

This FIH study has a double-blinded (investigator- and participant blinded), sponsor-open, randomized, single-ascending oral dose, up to 5 period crossover, placebo substitution design in 1 cohort (Cohort 1) of healthy adult participants. An optional cohort of healthy adult participants (Cohort 2) in up to 4 crossover periods, may be included to permit assessment of any of the following: repeat of a previously administered dose level; studying additional dose levels as dictated by the evaluated safety, tolerability, or PK of earlier dose levels; or any other assessment needed to meet the objectives of this study. A second optional cohort (Cohort 3) enrolling Japanese participants in up to 3 crossover periods, may be included.

A total of approximately 24 healthy adult participants will be randomized, up to approximately 10 in Cohort 1, up to approximately 8 in optional Cohort 2, and up to approximately 6 Japanese participants in optional Cohort 3. The actual number of Japanese participants may be adjusted based on emerging data or operational factors, with a maximum sample size of up to 8 participants. Each participant, depending on the cohort to which they are enrolled, will be randomized to receive up to 5 and 4 single doses of PF-06954522 for Cohorts 1 and 2, respectively, and up to 2 placebo doses. In each period, approximately 8 and 6 participants in Cohorts 1 and 2, respectively, will receive a single dose of PF-06954522, and approximately 2 participants will receive placebo. In the optional cohort of Japanese participants, each participant will be randomized to receive up to 2 single doses of PF-06954522 and 1 placebo dose. The actual dose levels and design of this optional cohort of Japanese participants will be decided based on emerging data. This cohort, if implemented, will not be part of dose escalation as the dose levels administered would have been investigated and deemed sufficiently safe in previous cohort(s). Full details will be provided to the investigator in writing, prior to dosing of this cohort. Participants who discontinue for non-safety reasons prior to completion of the study may be replaced, at the discretion of the PI and sponsor. The replacement participant(s) may or may not be required to complete all periods of the cohort in which they are participating at the discretion of the PI and sponsor.

Participants will be screened within 28 days of their first dose of study intervention (Period 1, Day 1). Participants will be admitted to the CRU on Day -1 of each study period and will remain in the CRU through at least the 72-hour assessments on Day 4. Participants may remain in the CRU after completion of Day 4 activities at the discretion of the investigator or if safety, tolerability, or PK data dictate the need to prolong confinement in the CRU. Participants will receive a single oral dose of PF-06954522 or placebo on Day 1 of each period.

Between each dose administration to a given participant there will be a washout interval of at least 7 days. The washout interval may be increased based on data emerging from previous cohorts/periods. Dose escalation will occur only after the previous dose level was demonstrated to be well tolerated with an acceptable safety profile based on review of the emerging safety and PK data (see Section 6.6.1). Dose levels will be escalated to bracket the expected clinical dose range, but the projected exposures will not exceed the predefined human exposure limits. An on-site follow-up visit and a telephone follow-up contact will take place 7-10 days and 28-35 days, respectively, after the last dose of study intervention in the final period, or after early discontinuation. At the discretion of the investigator, telephone follow-up contact may be substituted with an on-site visit in case of additional follow-up of open AEs or clinically significant laboratory findings. Therefore, the total planned duration of participation, from the Screening visit to the follow-up phone call, will be approximately 13 weeks for Cohort 1, 12 weeks for optional Cohort 2 and 11 weeks for optional Cohort 3 (if performed as a 3-way crossover).

Dosing of study intervention is anticipated to occur following a fast of at least 10 hours. Dose administration may also occur in the fed state (following a high-fat breakfast, see Section 5.3.2), in order to explore any potential food effect on PF-06954522 PK. If this assessment is conducted, it is anticipated that the study intervention will be administered in

the fed state in the last period of Cohort 1 at a dose level that has been previously administered fasted within the same cohort. The actual dose level may be adjusted based on emerging data. Design of randomization will be flexible to allow for participants who received active treatment or placebo in fasted state at the dose level of interest to also receive the same treatment in the food effect period (thus allowing within-participant comparisons of fed versus fasted for approximately 8 participants on active treatment, see Figure 1). If thought necessary to achieve study objectives (eg, to assess tolerability or exposure), study treatment may be administered in the fed state (high-fat or standard breakfast) during any of the study periods/cohorts.

A sample design overview is shown in Section 1.2. Treatment sequences, actual doses and dose increments may be adjusted during the study based on emerging safety, tolerability and PK data.

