1.3. Schedule of Activities

The SoA table provides an overview of the protocol visits and procedures. Refer to the STUDY ASSESSMENTS AND PROCEDURES section of the protocol for detailed information on each procedure and assessment required for compliance with the protocol.

The investigator may schedule visits (unplanned visits) in addition to those listed in the SoA table, in order to conduct evaluations or assessments required to protect the well-being of the participant.

Please refer to Appendix 10 for abbreviations used in the SoA table and associated footnotes. Note that the symbol \rightarrow denotes an activity that is continuous/ongoing for the indicated duration.

Table 1. Study Schedule of Assessments

Visit Identifier Abbreviations used in this table may be found in Appendix 10.	Screen							F/U Visit	F/U Contact	 Notes
Days Relative to Day 1	Day -28 to Day -2	Day -1	Day 1	Da	y 2	Day 3	Day 4	Days 8-11	Days 29-36	There are 5 periods in Cohort 1, 4 and 3 periods for optional Cohorts 2 and 3, respectively. Follow-up contact may occur via telephone contact and must occur 28 to 35 days after administration of the final dose of study intervention.
Hours After Dose			0	24	36	48	72			
Outpatient visit	X							X		F/U visit to occur 7-10 days after the final dose of study intervention (Period 4 only).
Informed consent	X									Informed consent should be obtained prior to undergoing any study-specific procedures. See Section 10.1.3 for additional information
CRU confinement		X	\rightarrow	\rightarrow	\rightarrow	→	X			Participants may be asked to remain at the CRU after completion of Day 4 activities at the discretion of the investigator or if safety, tolerability, or PK data (eg, t½ is longer than expected) dictate the need to prolong confinement in the CRU.
Discharge from CRU							X			
Demography	X									
Inclusion/exclusion criteria	X	X								Day -1 in Period 1 only. Review any changes from Screening.
Medical/medication history	X	X				_	_			Day -1 in Period 1 only. Review any changes from Screening.

Table 1. Study Schedule of Assessments

Visit Identifier Abbreviations used in this table may be found in Appendix 10.	Screen		Per	iod 1 to	Perio	d 5		F/U Visit		Early Discont	Notes

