6.1. Study Intervention(s) Administered

Study Intervention(s)		
Intervention Name	PF-06954522	Placebo
Туре	Drug	Drug
Use	Experimental	Placebo
IMP or NIMP/AxMP	IMP	IMP
Dose Formulation	Bulk powder for extemporaneous preparation of oral suspensions	Bulk powder for extemporaneous preparation of oral suspensions
Unit Dose Strength(s)	Planned suspension doses ranging from mg	0 mg
Dosage Level(s)	Single ascending doses CCI mg (see Section 1.2 and Section 4.3.4)	0 mg
Route of Administration	Oral	Oral

Study Intervention(s)		
Sourcing	Provided by the sponsor	Provided by the sponsor
Packaging and Labeling	Study intervention will be provided in bulk powder for extemporaneous preparation of oral suspensions. Each bottle will be labeled as required per country requirement.	Study intervention will be provided in bulk powder for extemporaneous preparation of oral suspensions. Each bottle will be labeled as required per country requirement.
SRSD	IB	IB

Study Arm(s)			
Arm Title	Cohort 1	Cohort 2 (Optional)	Cohort 3 (Optional)
Arm Description	Participants may receive up to 5 dose levels of PF-06954522 and matching placebo. Doses will be administered as oral suspensions as escalating single doses to be determined.	Participants may receive up to 4 dose levels of PF-06954522 and matching placebo. Doses will be administered as oral suspensions as escalating single doses to be determined.	Participants may receive up to 3 dose levels of PF-06954522 and matching placebo. Doses will be administered as oral suspensions as escalating single doses to be determined.

PF-06954522 and placebo will be provided by Pfizer as bulk powders for extemporaneous preparation of oral suspensions at the CRU.

 PF-06954522 or placebo oral suspensions will be extemporaneously prepared for single oral doses ranging from mg.

PF-06954522 and placebo will be presented to the participants in individual dosing containers.

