9.5. Sample Size Determination

A sufficient number of participants will be screened to achieve approximately 24 participants (up to 3 cohorts of up to approximately 10, 8 and 6 participants in Cohorts 1, 2, and 3, respectively) randomized. This sample size of approximately 24 participants for the entire study has been chosen based on the need to minimize first exposure to humans of a new chemical entity and the requirement to provide adequate safety, tolerability, and PK assessment at each dose level.

In each period of Cohort 1, approximately 8 participants are planned to receive PF-06954522, and 2 participants are planned to receive placebo; with all participants in Cohort 1 at the end of the study having received up to 5 doses of PF-06954522 and up to 2 doses of placebo.

In each period of Cohort 2, approximately 6 participants are planned to receive PF-06954522, and 2 participants are planned to receive placebo; with all participants in Cohort 2 at the end of the study having received up to 4 doses of PF-06954522 and up to 2 doses of placebo.

An optional cohort of Japanese participants (Cohort 3) with a target sample size of approximately 6 participants (approximately 4 receiving PF-06954522, approximately 2 receiving placebo in each period) may also be enrolled, if feasible. The actual number of Japanese participants may be adjusted based on emerging data or operational factors, with a maximum sample size of up to 8 participants (6 receiving PF-06954522 and 2 receiving placebo in each period).

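### Does Section 4.1's count of active doses per Cohort 3 participant need changing because it does not fit the optional 8-participant, three-period layout?

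*Protocol*

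**What the plan says.** Three features of optional Cohort 3 matter here.

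- **Doses per participant.** Protocol Section 4.1: "each participant will be randomized to receive up to 2 single doses of PF-06954522 and 1 placebo dose".
- **Size and split.** Protocol Section 9.5 gives a target of about 6 participants, about 4 on active and 2 on placebo per period. It then allows a "maximum sample size of up to 8 participants (6 receiving PF-06954522 and 2 receiving placebo in each period"). The synopsis and SAP Section 2.3 repeat the maximum and its split. Neither SAP Section 2.3 nor Section 9.5 gives a per-participant dose count for this cohort.
- **Periods.** Section 4.1: "A second optional cohort (Cohort 3) enrolling Japanese participants in up to 3 crossover periods, may be included". The Schedule of Activities notes: "There are 5 periods in Cohort 1, 4 and 3 periods for optional Cohorts 2 and 3, respectively". Section 4.1 gives the duration of participation as "11 weeks for optional Cohort 3 (if performed as a 3-way crossover").

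Three further statements bear on how these fit together. Section 4.1 doses everyone each time: "Participants will receive a single oral dose of PF-06954522 or placebo on Day 1 of each period". The arm table in Section 6.1, repeated in the synopsis, says of Cohort 3: "Participants may receive up to 3 dose levels of PF-06954522 and matching placebo". The sentence directly after the per-participant count in Section 4.1 reads: "The actual dose levels and design of this optional cohort of Japanese participants will be decided based on emerging data". The same paragraph adds that the investigator will get the full details in writing before this cohort is dosed, and that the cohort takes no part in dose escalation.

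**The concern.** Each of the three features looks firm, yet they cannot all hold at the maximum size over three periods. With 6 + 2 = 8, nobody sits out a period, so the active doses must be spread over the same eight people each time. A statistician building the randomisation schedule for that layout would have to break either the per-participant count in Section 4.1 or the 6:2 split in Section 9.5.

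What would be at stake is the stated number of active doses per person in a first-in-human study. A participant could be allocated one more active dose than Section 4.1 describes, and no placebo period. A reader might also worry that losing within-participant placebo data weakens the safety comparison in this cohort.

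**Working it through.** **Inputs**

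| Quantity | Value | Source |
|---|---|---|
| Active doses per participant | up to 2 | Protocol 4.1 |
| Placebo doses per participant | 1 | Protocol 4.1 |
| Target size and split | 6, as 4:2 | Protocol 9.5 |
| Maximum size and split | 8, as 6:2 | Protocol 9.5, synopsis, SAP 2.3 |
| Periods | up to 3 | Protocol 4.1; 3 in the Schedule of Activities |
| Doses per participant per period | 1 | Protocol 4.1 |

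**Formulas.** Active doses needed = (active per period) × (periods). Active doses allowed = 2 × (participants). Placebo doses needed = 2 × (periods).

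**The plan's own target first.** Six participants, three periods:
- active needed 4 × 3 = 12, allowed 2 × 6 = 12;
- placebo needed 2 × 3 = 6, and one each gives 6.

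Both counts agree exactly, so the wording in Section 4.1 matches the target layout.

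**Maximum size, three periods.** Eight participants:
- active needed 6 × 3 = 18, allowed 2 × 8 = 16, an excess of 2;
- placebo needed 2 × 3 = 6 for eight people, so at least 8 − 6 = 2 get none and receive three active doses.

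The smallest departure is six people on 2 active + 1 placebo and two people on 3 active: 6 × 2 + 2 × 3 = 18. Giving all eight 2 active + 1 placebo yields 16 active and 8 placebo doses, an average of 16/3 = 5.33 and 8/3 = 2.67 per period instead of 6 and 2.

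**Maximum size, two periods.** Active needed 6 × 2 = 12 against 16 allowed. No conflict.

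**Where the conflict begins.** With 2 on placebo in each of three periods, the count fits when 3(n − 2) ≤ 2n, that is n ≤ 6.

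**The arm table.** For Cohorts 1 and 2 the same sentence gives 5 and 4 dose levels, which equal the per-participant maxima in Section 4.1. Read the same way, the 3 for Cohort 3 is a per-participant figure: 3 × 8 = 24, and 18 fits. Read as a cohort total, it gives no relief. The first reading removes the shortfall but differs from the 2 in Section 4.1.

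**Does any result use the count?**
- Protocol 9.1 and SAP 5.1 plan no hypothesis test, and Section 9.5 does not base the sample size on power.
- SAP 5.2 leaves this cohort out of the pooled placebo group, and SAP 6.3.4 reports the cohort separately.
- The safety set is analysed by the product actually received (Protocol 9.2, SAP 4).
- The only model specified in detail is the food-effect model (SAP 6.3.2), which compares fed with fasted active doses and does not involve placebo.
- Placebo observations over three periods are 2 × 3 = 6 at either size.

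**The case for a change.** The best case for a change is that the figures are explicit. Section 9.5 hedges the 4:2 target as approximate but does not hedge the 6:2 split. The three-period version is the only Cohort 3 layout given a duration. A clause deferring the design does not make stated numbers agree, and Section 4.1 does not say that its count applies only to the smaller cohort. Doses per person is an exposure figure in a first-in-human study, and one clause would settle it. Replacement participants do not help, because Section 4.1 allows them only after someone discontinues for non-safety reasons.

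Much of this stands. The 18 against 16 is correct, the two statements do conflict for that layout, and the arm table adds a second loose figure. The step from there to a needed change does not stand. The deferral clause sits beside the count it qualifies and covers the design as well as the dose levels, and Section 4.1 also lets treatment sequences be adjusted on emerging data. The count is therefore most naturally read as describing the target layout. The worry about exposure is limited by the protocol's own terms: Cohort 3 would receive only dose levels already studied and judged sufficiently safe in earlier cohorts. How many active doses a participant should receive is a clinical decision for the sponsor, and nothing here argues for one figure over another.

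**Conclusion.** No change to the plan follows. Section 4.1 states a per-participant count that fits the target layout exactly and was not restated for a contingent larger one. The discrepancy is 2 active doses out of 18, affecting at least 2 of 8 participants. It appears only if three things coincide: the optional cohort is opened, it is enlarged to 8, and it runs for three periods.

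If that layout is chosen, Protocol Sections 4.1, 6.1 (with the synopsis arm table) and 9.5 must be reconciled, and the sponsor decides which figure gives way. The protocol already provides the step at which this happens, since the cohort's details must be written down before dosing and a schedule cannot be produced without settling the point. SAP Section 2.3 needs no edit unless the 6:2 split itself changes. Amending now would alter no estimate, summary, power figure or placebo count.

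This rests on four assumptions: exactly 2 participants receive placebo in every period; all eight complete every period; no replacements enter; and the deferral in Section 4.1 covers the allocation of sequences as well as the choice of dose levels. If the last were read more narrowly, the inconsistency would still be editorial, with the same size and no effect on the analysis.
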